2 SB1 AG059458-04A1
April 12, 2022

Pre-Screening Procedures:

For Phase IIA, participants will be recruited through 1) UCSF Memory and Aging Center, 2) other clinics, and 3) caregiver organizations, such as the Alzheimer's Association (including those contacted by Recruitment Partners, which is a company that specializes in community-level partnerships to identify potential research participants). Recruitment efforts are aimed at the caregivers of individuals with neurodegenerative disease using three types of materials: (a) flyers, (b) a description of the study that was prepared originally for clinicaltrials.gov, and (c) a recruitment video. The video (approximately 2.5-minute) is used to describe this research study and introduce the in-home technology system. This video would be accessible in emails or online links provided by our research team to groups/organizations and caregivers who wish to learn more about the study. Caregiver groups/organizations may elect to embed the video link in newsletters, or show the video to interested caregivers who may qualify to participate. All recruitment materials describe the general nature and goals of the research and provide information about what participation involves and monetary compensation. The Berkeley research team is listed as the source for additional information and addressing questions in all materials.

Initial Encounter:

Potential participants will be caregivers of PWD and will either be contacted via UCSF by [name] for screening, or recruited via flyer in clinics or other locations where caregivers gather (e.g., dementia support groups). Eligible caregivers will be invited to participate in the study and will schedule an installation with members of the Berkeley Psychophysiology Laboratory. Prior to installation, participants will be sent a link to complete a set of questionnaires. For participants not recruited via UCSF, this will include "Screening Questionnaire: Information about person receiving care", which obtains additional information about the needs of the person receiving care. A member of the UC Berkeley research team listed on this protocol will determine the installation and start date for that participant. For those caregivers recruited by flyers posted in dementia clinics and other locations that current caregivers are likely to visit, we would receive permission for all postings and would comply with any rules that a given clinic or location may have. All interested caregivers recruited via flyers at clinics or other locations, and via online study description would initiate contact with our research team (i.e., we would not ask them to write down any personal information on flyers, or sign up on any forms to be contacted).

Caregivers who complete the IIA study in the control group will be provided with an opportunity at the end of the 9-month study to use a fully-functioning Presence Care system at no cost if they agree to complete questionnaires for an additional 9-month period (completing questionnaires at 12-months, 15-months, and 18-months). These caregivers would be recruited by the UC Berkeley research team just before the completion of their IIA participation. Participation is

completely optional and caregivers who decline participation upon receipt of our group's email will not be penalized in any way.

Consent:

For most participants, we will use Qualtrics to administer the initial screening questionnaire, online consent form (which describes all study procedures involving installation and questionnaires), and all subsequent questionnaires. Online consent requires participants to click on a box stating, "By clicking here, I indicate that I have read the above consent form and agree to take part in the research."

Baseline Outcome Assessment:

Once caregivers complete the screening questionnaire, a member of the Berkeley team will send the caregiver their consent form via a Qualtrics link, along with a link to the first questionnaire administration will be sent for the caregiver. Identical Qualtrics questionnaires will be sent via email to caregivers in both research conditions at baseline, 3 months, 6 months and 9 months. The four sets of questionnaires will be identical, except: a) the baseline questionnaire will also include a contact information form and "Information about person receiving care," and b) the 3-month, 6-month, and 9-month questionnaires will also include questions regarding the usefulness of Presence Care in their homes.

Randomization:

Fifty percent of the caregivers will be randomly assigned to the "experimental in-home technology" condition of Presence Care and the remaining 50 percent of caregivers will be assigned to the "limited control" condition. Randomization of participants in each group will be determined by members (i.e., graduate students listed in this protocol) of the research team and staff members completing the installation will not be aware of which group the caregivers are assigned to. Immediately following the installation, [name], an employee of People Power, will remotely (i.e., through People Power's online system) activate Presence Care and all sensors for those in the "experimental" condition. [name] will only activate water alerts in the "limited control" group.

Outcome Measures:

All caregivers—regardless of randomized study condition—complete questionnaires on four separate occasions during this study: baseline, 3-months, 6-months, and 9-months. The four outcome measures include are: (a) Zarit Burden Interview-Short Form, a questionnaire measuring caregiver burden (Zarit, Reever, & Bach-Peterson, 1980). 12 items are rated on 0-4 scale. Range: 0-48. No subscales. Higher scores represent worse outcomes; (b) Center for Epidemiological Studies Depression Scale (CES-D), a questionnaire measuring depression (Radloff, 1977). 20 items are rated on a 0-3 scale and summed (range = 0-60). There are no subscales. Higher scores represent worse outcomes. The clinical cut-off is usually set at a score

of 16; (c) Beck Anxiety Inventory (BAI), a questionnaire measuring anxiety (Beck, Epstein, Brown, & Steer, 1988). 20 items are rated on a 0-3 scale and summed (range= 0-60). Higher scores indicate worse outcomes. There are no subscales. A score greater than 36 is considered to be clinically significant; and (d) Satisfaction with Life Scale, a questionnaire measuring overall life satisfaction and well-being (Diener, Emmons, Larsen, & Griffin, 1985). 5 items scored on a 1-7 scale and summed (Range = 5-35). Lower scores indicate worse outcomes. A score of 20 is considered neutral with higher scores considered increasingly more satisfied and lower scores considered increasingly more dissatisfied.

Contact initiated by study staff

Identical Qualtrics questionnaires will be sent via email to caregivers in both research conditions at baseline, 3 months, 6 months and 9 months. The initial questionnaire to be completed prior to installation will be identical to the follow-up questionnaires, except with the addition of a contact information form and "Information about person receiving care", and the 3, 6, and 9 month questionnaires will also have questions regarding the usefulness of Presence Care in their homes. Questions ask about caregivers' health and the ease of use of the equipment. Upon completion of the baseline questionnaire and installation of the Presence Care system, caregivers will be mailed a \$100 check. Upon completion of the final questionnaire at 9 months, caregiver participants will be mailed a \$75 check to compensate for their time completing questionnaires. A member of the research team will contact the caregivers to determine if they would like the system uninstalled by the research staff members of the Berkeley Psychophysiology Laboratory (in which case a time and date will be determined), or keep any and all sensors, devices, or equipment in their home. For those who choose to keep equipment or devices, they will not be charged any cost and we will end our data collection of any related devices and will not ask that they complete any additional questionnaires regarding their usage of the system, sensors, or equipment (i.e., their participation in this study is complete). Caregivers randomly assigned to the limited control condition will be offered an opportunity to enroll in an additional 9-month study. Those who were originally assigned to a limited "control" group would have all sensor alerts activated. [name], of People Power, would remotely activate Presence Care features (e.g., alerts for door entry/exit sensors and stove usage) for those originally assigned to Group 1 (i.e., the limited control condition), as necessary. Thus, there would not be a need for additional home visits in order to begin participation. Caregivers in the limited-control condition who opt to continue participation would be asked to complete questionnaires at months 3, 6, and 9 (3 additional questionnaires). Following the completion of this additional 9 month study, caregivers will be mailed a check for \$75 to compensate for their time and effort.

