## Statistical Analysis Plan

### Primary Outcomes

All caregivers—regardless of randomized study condition—complete questionnaires on four separate occasions during this study: baseline, 3-months, 6-months, and 9-months. The four outcome measures include changes over the 9-month study period for the following scales: Zarit Burden Interview-Short Form, a questionnaire measuring caregiver burden (Zarit, Reever, & Bach-Peterson, 1980). 12 items are rated on 0-4 scale. Range: 0-48. No subscales. Higher scores represent worse outcomes; Center for Epidemiological Studies Depression Scale (CES-D), a questionnaire measuring depression (Radloff, 1977). 20 items are rated on a 0-3 scale and summed (range = 0-60). There are no subscales. Higher scores represent worse outcomes. The clinical cut-off is usually set at a score of 16; Beck Anxiety Inventory (BAI), a questionnaire measuring anxiety (Beck, Epstein, Brown, & Steer, 1988). 20 items are rated on a 0-3 scale and summed (range= 0-60). Higher scores indicate worse outcomes. There are no subscales. A score greater than 36 is considered to be clinically significant.; and Satisfaction with Life Scale, a questionnaire measuring overall life satisfaction and well-being (Diener, Emmons, Larsen, & Griffin, 1985). 5 items scored on a 1-7 scale and summed (Range = 5-35). Lower scores indicate worse outcomes. A score of 20 is considered neutral with higher scores considered increasingly more satisfied and lower scores considered increasingly more dissatisfied.

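### The plan lets a control-only offer of the free full system reach caregivers before their 9-month questionnaire, because no timing rule ties the offer to its submission

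*Protocol*

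**What the plan says.** The protocol describes the extension offer in two places.

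- **Initial Encounter.** "Caregivers who complete the IIA study in the control group will be provided with an opportunity at the end of the 9-month study" and the opportunity is "to use a fully-functioning Presence Care system at no cost if they agree to complete questionnaires for an additional 9-month period". The timing of the approach is then given: "These caregivers would be recruited by the UC Berkeley research team just before the completion of their IIA participation". The approach is by email, since "caregivers who decline participation upon receipt of our group's email will not be penalized in any way". Only the control arm is approached.
- **Contact initiated by study staff.** The text runs in this order: the final questionnaire and its payment ("Upon completion of the final questionnaire at 9 months, caregiver participants will be mailed" a check), a contact about removing or keeping the equipment, and then the offer: "Caregivers randomly assigned to the limited control condition will be offered an opportunity to enroll in an additional 9-month study". No sentence says that the offer must wait for the questionnaire.

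On outcomes, the SAP (Primary Outcomes) says: "The four outcome measures include changes over the 9-month study period for the following scales". All four scales (burden, depression, anxiety and life satisfaction) are caregiver self-reports collected at baseline and at 3, 6 and 9 months. The protocol's Randomization section keeps installation staff unaware of allocation and says nothing about caregivers. Controls have only water alerts activated.

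**The concern.** Staff who follow the Initial Encounter text literally may send the email shortly before the 9-month questionnaire is answered. A control caregiver would then rate mood, burden and life satisfaction just after being promised a fuller system at no cost, and no experimental caregiver would have had a comparable message. Relief at coming help could improve the ratings; disappointment at having had the lesser version could worsen them.

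A shift in one arm at one visit enters the group-by-time interaction that the SAP uses to judge treatment effects. A departure confined to month 9 would be visible against earlier visits, but its cause could not be established. Neither of the SAP's two missing-data approaches addresses a shift in observed scores.

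**Working it through.** **Order of events.** Initial Encounter places recruitment shortly before IIA participation is complete. The contact section narrates the offer after the last questionnaire. The only explicit statement that participation is complete comes in the contact section, after the equipment decision, for caregivers who keep devices. So the end of participation could mean the 9-month questionnaire or the later equipment step. On the first meaning the email precedes the last outcome assessment; on the second it may follow it. The text permits both.

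**The plan's own figure.** The SAP states .80 power with N = 80, four measurements, a medium effect and p = .05. It gives no numerical effect size or correlation, so f = .25 and ρ = .5 are assumptions. For the between-group test:

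- λ = N f² m / (1 + (m − 1)ρ) = 80 × .0625 × 4 / (1 + 3 × .5) = 20 / 2.5 = 8, with 1 and 78 df.
- Power = .798, which reproduces .80. It is .893 at ρ = .3 and .668 at ρ = .8.

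The timing of the offer does not alter this figure.

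**Illustration of a control-only shift b at month 9.** Inputs: 40 per arm (80 randomized 1:1, from the SAP); ρ = .5 and b = .1 or .2 SD are assumed. The value b is the average over the whole control arm: .2 SD means .2 in every control, or .4 in half of them (.5 × .4 = .2).

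*Baseline-adjusted contrast at month 9.* SE = √(2/40 × (1 − .5²)) = √.0375 = .194 SD.

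| Shift b | b / SE | False-positive rate, normal approximation | Same, noncentral t |
|---|---|---|---|
| 0 | 0 | .05 | .05 |
| .1 | .52 | .081 | .080 |
| .2 | 1.03 | .178 | .175 |

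The test is two-sided, so these rates are the same whichever way the controls move. At ρ = .7 the noncentral t gives .095 and .236.

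*Power at month 9 for a true effect of .5 SD (noncentral t, ρ = .5).* Without a shift it is .72. If the offer improves control scores by .1 or .2 SD, it falls to .53 or .33. If it worsens them, it rises to .86 or .95, and the estimated benefit is inflated. The distortion is .1/.5 = 20% or .2/.5 = 40% of the effect.

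*Group-by-time interaction, three visits, shift at the last only.* The between-arm differences are (0, 0, b), and the sum of squares about their mean is 2b²/3.

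- λ = (40/2) × (2b²/3) / (1 − ρ), with 2 and 156 df.
- b = .1: λ = 20 × .00667 / .5 = .27; rejection rate .070.
- b = .2: λ = 20 × .02667 / .5 = 1.07; rejection rate .137.

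With four visits the rates are .068 and .129.

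**The case against.** The strongest reply is that the passages can be read together without conflict. Initial Encounter also puts the opportunity at the end of the nine months and addresses caregivers who complete the study, and the contact section puts the offer last. An offer made around the equipment decision also fits the aim of avoiding another home visit. This stands as far as it goes: the order is open. A reader might infer that the email is bound to precede the 9-month questionnaire, but the documents do not say so. Nor do they exclude it, and the only wording that times the approach itself points to before completion.

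A reader might also infer that the email unblinds the control arm. The documents do not support that. They claim no caregiver blinding, controls live for nine months with water alerts only, and the consent text is not available to show what caregivers were told. Many may know or guess their arm. What remains is that even a caregiver who knows the allocation receives a one-arm promise of help close to a self-report.

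A third inference is that the offer would raise 9-month completion among controls, because it goes to those who complete the study. That is speculative: both arms are paid \$75 after the final questionnaire, and nothing describes the email as a prompt to answer it.

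Finally, the calculated rates depend on assumed shifts. Individual reactions may differ in direction and partly cancel, and the stand-alone 9-month contrast gives higher false-positive rates than the interaction the SAP tests. Both points are correct.

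**Conclusion.** The concern holds as a gap in timing. The plan allows an offer made to controls only to come before the last self-report of all four primary outcomes, and nothing in either document prevents it. Any resulting shift would affect month 9 alone and could go either way.

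Its size cannot be determined from the documents. With 40 per arm, a correlation of .5 and an assumed arm-average shift of .1 or .2 SD, the false-positive rate would be about .08 or .18 for the adjusted 9-month contrast and about .07 or .14 for the interaction. These figures show sensitivity to a shift; they are not an estimate of this trial's error rate. The plan's sample size and stated power are not called into question. The change should still be made, because it removes an avoidable one-arm influence on the primary outcomes at very little cost.

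**What to change.** In the protocol's Initial Encounter section, replace the timing clause with a condition that control caregivers are approached only after the 9-month questionnaire has been submitted or its response window has closed. Put the same condition beside the offer in the section on contact initiated by study staff, so that the two agree. The available text gives no response window for that questionnaire, so one would need to be set.

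The cost is a sentence in each place and a short delay in sending the email. The offer can still be made at or before the equipment contact, so the system stays in place and can be activated remotely without a home visit. The first extension questionnaire is not due until month 12. Sample size, power and analysis are unchanged.

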## Statistical Analysis Plan

### Primary Outcomes

All caregivers—regardless of randomized study condition—complete questionnaires on four separate occasions during this study: baseline, 3-months, 6-months, and 9-months. The four outcome measures include changes over the 9-month study period for the following scales: Zarit Burden Interview-Short Form, a questionnaire measuring caregiver burden (Zarit, Reever, & Bach-Peterson, 1980). 12 items are rated on 0-4 scale. Range: 0-48. No subscales. Higher scores represent worse outcomes; Center for Epidemiological Studies Depression Scale (CES-D), a questionnaire measuring depression (Radloff, 1977). 20 items are rated on a 0-3 scale and summed (range = 0-60). There are no subscales. Higher scores represent worse outcomes. The clinical cut-off is usually set at a score of 16; Beck Anxiety Inventory (BAI), a questionnaire measuring anxiety (Beck, Epstein, Brown, & Steer, 1988). 20 items are rated on a 0-3 scale and summed (range= 0-60). Higher scores indicate worse outcomes. There are no subscales. A score greater than 36 is considered to be clinically significant.; and Satisfaction with Life Scale, a questionnaire measuring overall life satisfaction and well-being (Diener, Emmons, Larsen, & Griffin, 1985). 5 items scored on a 1-7 scale and summed (Range = 5-35). Lower scores indicate worse outcomes. A score of 20 is considered neutral with higher scores considered increasingly more satisfied and lower scores considered increasingly more dissatisfied.

### Statistical Methods

*Design:* Caregivers will be randomized into two groups: Experimental In-Home Technology System and Limited In-Home Technology System. Subjects will be randomized 1:1. Randomization of participants in each group will be determined by members (i.e., graduate students listed in this protocol) of the research team and staff members completing the installation will not be aware of which group the caregivers are assigned to. With a total N of 80 caregivers in two conditions and measures repeated four times, a comparison between groups using ANOVA will have .80 power to detect a medium effect size at  $p=.05$ .

*Analysis:* Descriptive statistics will be used to summarize all the clinical characteristics and demographic outcomes. These will be summarized overall, by treatment group, by assessment time, and by treatment group and time. Continuous variables will be summarized using means, standard deviations, and ranges. Categorical data will be summarized by number and percent. To evaluate the treatment effects, we will use repeated measures ANCOVAs. The respective baseline measure of each outcome variable will be included as a covariate in the appropriate analysis (e.g., baseline depression scores from the baseline measurement of the CES-D, will be used as a covariate in examining treatment effects of depression). The other predictors will be treatment group, and time (baseline, 6-months, and 9- months for caregiver outcomes). To

evaluate treatment effects, an interaction term between treatment group and time will be included to examine treatment group-related differences controlling for baseline to later assessments for each outcome. Each significant interaction will be followed up with paired t-tests to examine treatment differences at each set of time points. Although this study involves 4 outcomes, we do not plan formal multiple comparison adjustments if the results fit a coherent pattern that is consistent with the context of similar studies. In this case, each result will reinforce the other, rather than detracting from one another, as required by formal multiple comparisons adjustments such as Bonferroni. Conversely, if only one or a very few measures reach statistical significance and their directions and/or magnitudes do not coherently fit with our prior expectations, then we will note that the result(s) with  $p < 0.05$  lack plausibility and could be due to chance, despite meeting the conventional cutoff for statistical significance.

*Missing Data:* If subjects either cannot or refuse to complete surveys we will use a sensitivity analysis approach in dealing with these missing data by performing analysis with 2 versions of scores: 1) with missing item interpolated using mean replacement by group, and 2) only using responses with 0% missing data. If the results differ for the two approaches, then we will report on the differences.

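### The .80 power figure counts the pre-installation baseline among its four measures; for d=.5 at the follow-up visits, the ANOVA it names has about .55

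*SAP*

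**What the plan says.** The power statement is one sentence in the Design paragraph of the SAP's Statistical Methods. For 80 caregivers in two arms, it states that with "measures repeated four times, a comparison between groups using ANOVA will have .80 power to detect a medium effect size", at p=.05. Allocation is equal: "Subjects will be randomized 1:1". The sentence gives no number for the medium effect, no correlation between repeated measures and no allowance for dropout.

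The SAP's Primary Outcomes section identifies the four measures. Caregivers "complete questionnaires on four separate occasions during this study: baseline, 3-months, 6-months, and 9-months". The Protocol (Contact initiated by study staff) fixes the timing of the first one: "The initial questionnaire to be completed prior to installation will be identical to the follow-up questionnaires", apart from some added forms. The Protocol's Randomization section has the system switched on remotely, according to arm, once installation is done.

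The Analysis paragraph of the SAP plans something other than the ANOVA in the power sentence. It plans repeated measures ANCOVAs with the baseline score as covariate, and it judges treatment by a group-by-time interaction. Its list of time levels is baseline, 6 months and 9 months.

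**The concern.** The baseline questionnaire comes before installation, and the arms differ in what is activated only after it. Under randomization the expected arm difference at baseline is therefore zero. A between-groups comparison of the four-visit average mixes one null difference with three treated ones, so a constant follow-up effect is diluted to three quarters of its size. The usual power formula for a between-groups factor with four repeated measures makes no such reduction. It takes the effect size as applying to the average of all four.

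This is the only figure supporting N=80. A reader who takes medium to mean half a standard deviation once the system is running will believe the named comparison has a four-in-five chance of detecting it. Under that reading the chance is a little over one half.

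**Working it through.** **Inputs from the documents.** N=80, 1:1 (40 per arm); m=4 measures including baseline; alpha .05; test: "a comparison between groups using ANOVA", that is, the group main effect with 1 and 78 degrees of freedom.

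**Assumptions.** Medium is f=.25, equivalent to d=.5 for two equal groups. The correlation rho is the same between all pairs of visits. Data are complete.

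**1. The stated figure.** With lambda = N f² m / (1+(m−1)rho) and a noncentral F(1,78):

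- rho=.5: lambda = 80 × .0625 × 4 / 2.5 = 8.0, power .798.
- rho=.495 gives .80 exactly.
- Variants that do not give .80: a single measure (.60), three measures at rho=.5 (.77), a one-sided test (.88).

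**2. The same test with no difference at baseline.** Differences of 0, .5, .5, .5 average to 1.5/4 = .375, so f = .375/2 = .1875. At rho=.5, lambda = 8.0 × (3/4)² = 4.5 and power is .554. Simulation with 20,000 runs gives .796 for step 1 and .555 for step 2.

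**3. Dependence on the correlation.**

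| rho | d=.5 averaged over all four visits | d=.5 at 3, 6, 9 months; 0 at baseline | Follow-up d needed for .80 |
|---|---|---|---|
| .30 | .89 | .67 | .58 |
| .45 | .82 | .58 | .65 |
| .50 | .80 | .55 | .67 |
| .54 | .78 | .53 | .68 |
| .70 | .71 | .47 | .74 |

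Only the rows with rho between .45 and .54 are compatible with a stated figure of roughly .80 (.78 to .82). The relevant range for the reduced power is therefore .53 to .58. The outer rows show sensitivity only.

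**4. What makes .80 true.** The four-visit average must be .5, so the follow-up difference must be .5/.75 = .67. Differences of 0, .67, .67, .67 give lambda 8.0 and power .798 again.

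**5. Power of other tests for the same step effect (0, then d=.5), N=80.**

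- *Group by time over baseline, 6 and 9 months*, computed without the covariate. Differences 0, .5, .5 have mean .333 and squared deviations summing to .1667. lambda = (N/4) × .1667/(1−rho) = 20 × .1667/.5 = 6.67, F(2,156), power .62. At rho=.3 it is .48 and at rho=.7 it is .85.
- *Baseline-adjusted group effect on the mean of the three follow-ups.* The residual variance is (1+2rho)/3 − rho² = .6667 − .25 = .4167. lambda = 20 × .25/.4167 = 12.0, F(1,77), power .93. At rho=.3 it is .91 and at rho=.7 it is .98.

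**The case against.** The strongest reply is that the .80 contains no arithmetic error. For a between-groups factor, f is conventionally defined on group means averaged over the repeated measures. Read that way, .80 is correct with f=.25 and rho=.5, and .55 appears only once medium is tied to each follow-up visit. This stands. A reader might go further and infer that the .80 rests on an effect this design cannot produce, or that it requires a treatment difference at baseline. The documents do not support that: a follow-up difference of about .67 SD with none at baseline also yields it. What remains is that .67 is one third larger than the conventional medium, and the SAP's phrase "to detect a medium effect size" does not tell the reader so.

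A second reply is that no trial result will come from this ANOVA, because the SAP evaluates treatment by ANCOVA with a group-by-time term. This also stands, and it limits the consequence. The .55 describes the comparison in the power sentence, not the planned analysis. A reader might infer that the planned analysis has less power still. The figures do not show that: at rho=.5 the group-by-time test has about .62 for the same effect, and a baseline-adjusted group effect about .93.

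A third reply is that the effect size and correlation are the reviewer's assumptions. They are, because the SAP supplies neither. The correlation was chosen because it recovers the stated figure, and the exact calculation behind the .80 is not documented.

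**Conclusion.** The point holds in a limited form. The documents' own schedule makes one of the four measures a pre-treatment score, and the power sentence does not say whether its medium effect is an average that includes that score or a difference at follow-up. If it is d=.5 at 3, 6 and 9 months, the named ANOVA has about .55 power (.53 to .58 where the stated figure stays near .80). If .80 is to stand, the detectable follow-up difference is about d=.67. Both statements assume f=.25 as the meaning of medium, a common correlation near .5 and no missing data; dropout would lower all the figures.

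This does not show that the trial is too small. Whether 80 caregivers suffice depends on the test finally used, and the .80 does not describe the test now planned.

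**What to change.** Rewrite the power sentence in the SAP's Design paragraph so that it states the numeric effect size, the visits at which it applies, the assumed correlation and the complete-data assumption.

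- If the four-measure between-groups ANOVA is kept as the basis, give about .55 power for d=.5 at follow-up, or a detectable follow-up difference of about d=.67, at correlation .5.
- State power for the treatment test that will be used. For the group-by-time test over baseline, 6 and 9 months this is about .62 at correlation .5 for a step effect of d=.5.
- The figure of about .93 (.91 to .98 for correlations .3 to .7) may be quoted only if the treatment test is also changed to the baseline-adjusted group effect on the post-baseline scores, with baseline removed as a level of time. Removing baseline from time while still testing the interaction would not do: an effect that is constant over follow-up produces no interaction, and power would equal the .05 alpha level.

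The first two items cost a rewritten sentence and a less favourable stated figure. The third also requires a change to the Analysis paragraph. None needs extra caregivers.
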